## **13. ETHICAL CONSIDERATIONS AND COMPLIANCE WITH GOOD CLINICAL PRACTICE**

### **13.1 Ethical Considerations**

The rights, safety and well-being of the trial subjects are the most important considerations and should prevail over interests of science and society.

Study personnel involved in conducting this trial will be qualified by education, training, and experience to perform their respective task(s).

This trial will not use the services of study personnel where sanctions have been invoked or where there has been scientific misconduct or fraud (e.g., loss of medical licensure, debarment).

Systems with procedures that assure the quality of every aspect of the study will be implemented.

### **13.2 Statement of Compliance**

This clinical study will be conducted using cGCP, as delineated in *Guidance for Industry: E6 Good Clinical Practice Consolidated Guidance*, and according to the criteria specified in this study protocol. Before study initiation, the protocol and the informed consent, subject recruitment materials/process (e.g., advertisements), and any other written information to be provided to subjects will be reviewed and approved by an appropriate EC or IRB, and NIAID/NIDDK. The investigator or sponsor should also provide the IRB/EC with a copy of the IB or product labeling and information to be provided to subjects and any updates. Any amendments to the protocol or to the consent materials must also be approved by the IRB/EC and submitted to the applicable Health Authorities before they are implemented.

### **13.3 Informed Consent and Assent**

Preparation of the consent form is the responsibility of the investigator, and must include all elements required by ICH, GCP, and applicable regulatory requirements, and must adhere to GCP and to the ethical principles that have their origin in the Declaration of Helsinki. The consent form must also include a statement that the sponsor and regulatory authorities have direct access to subject records. Consent materials for subjects who do not speak or read English must be translated into the subjects' appropriate language.

The informed consent form must be revised whenever important new safety information is available, whenever the protocol is amended, and/or whenever any new information becomes available that may affect participation in the trial.

A copy of the informed consent will be given to a prospective subject for review. The attending physician, in the presence of a witness if required by the IRB, will review the consent and answer questions. The prospective subject will be told that being in the trial is voluntary and that he or she may withdraw from the study at any time, for any reason.

### **13.4 Privacy and Confidentiality**

A subject's privacy and confidentiality will be respected throughout the study. Each subject will be assigned a sequential identification number, and these numbers rather than names will be used to collect, store, and report subject information.

### **13.5 Mentally Impaired or Incapacitated Subjects**

Investigators should determine whether or not a mentally impaired or incapacitated subject is capable of giving informed consent. If the subject is deemed mentally competent to give informed consent, the investigator should follow standard procedures. If the subject is deemed not to be mentally competent to give informed consent, he/she is not eligible to participate in this study.

Subjects who are involuntarily hospitalized because of mental illness will not be enrolled in this clinical trial.

### **13.6 Other Circumstances**

Prisoners or individuals who are compulsorily detained for treatment of either a psychiatric or physical (e.g., infectious disease) illness will not be enrolled in this clinical trial.

### **13.7 Illiterate Subjects**

If the subject or legally acceptable representative is unable to read, a reliable and independent witness should be present during the entire informed consent discussion. The choice of the witness must not breach the subject's rights to confidentiality. A reliable independent witness is defined as one not affiliated with the institution or engaged in the investigation. A family member or acquaintance is an appropriate independent witness. After the subject or legally acceptable representative orally consents and has signed, if capable, the witness should sign and personally date the consent form attesting that the information is accurate and that the subject or legally acceptable representative has fully understood the content of the informed consent agreement and is giving true informed consent.

### **13.8 Records Retention**

The investigator must retain investigational product disposition records, copies of CRFs (paper or electronic files), and source documents for the maximum period required by applicable regulations and guidelines, or institution procedures, or for the period specified by the sponsor, whichever is longer. The investigator must contact the Sponsor prior to destroying any records associated with the study.

If the investigator withdraws from the study (e.g., relocation, retirement), the records shall be transferred to a mutually agreed upon designee (e.g., another investigator, IRB).

## **14. PUBLICATION POLICY**

The CIT policy on the publication of study results will apply to this trial.

**Appendix 1: Year One Schedule of Events**

Time points (in days relative to transplant)	SCR	WL / BL 	0 	3	4	7	14	21	28	56	75	84	112	140	168	196	224	252	280	308	336	365	
Visit Number	01	02	03	03a	04	05	06	07	08	09	10	11	12	13	14	15	16	17	18	19	20	21	
Visit Windows (in days)	N/A	N/A	N/A	N/A	N/A	+/-2	+/-2	+/-2	+/-3	+/-3	+/-5	+/-3	+/-3	+/-3	+/-3	+/-5	+/-5	+/-5	+/-5	+/-5	+/-5	+/-5	
Equivalent Week	N/A	N/A	N/A	N/A	N/A	W1	W2	W3	W4	W8	N/A	W12	W16	W20	W24	W28	W32	W36	W40	W44	W48	W52	
GENERAL ASSESSMENTS																							
Informed Consent	X 	X 																					
Med/Diabetes Hx & Demographics	X																						
Eval of Inclusion / Exclusion	X	X																					
Mammogram (females >35)	X	X-yrly																					
Retinopathy Evaluation 	X	X-yrly 																				X	
Physical Exam	X	X-yrly	X			X	X	X	X	X	X		X	X		X			X			X	
QOL		X-q3mo									X					X			X			X	
Chest X-Ray	X	X-yrly																				X	
Abdominal US (Pelvis/Liver)	X	X-yrly				X																X	
ECCG	X	X-yrly																				X	
Cardiac Stress Test or Angiogram	X																						
PPD	X	X-yrly																				X	
AE/Hypo Event/Toxicity Assess		X	X		X	X	X	X	X	X	X	X	X	X	X	X	X	X	X	X	X	X	X
LOCAL LABORATORY ASSESSMENTS																							
CBC (WBC + Diff & Plat)	X	X-q6mo	X			X	X	X	X	X	X		X	X		X			X			X	
Chemistry 	X	X-yq6mo	X			X	X	X	X	X	X		X	X		X			X			X	
Lipids	X	X-q6mo									X					X			X			X	
Thyroid Function (TSH)	X	X-yrly																					
Pregnancy test (WOCBP)	X	X 		X 			X 		X 	X 		X 	X 	X 	X 	X 	X 	X 	X 	X 	X 	X 	
Serology  (Hep B/C, HIV)	X	X-yrly																				X	

Time points (in days relative to transplant)	SCR	WL / BL 	0 	3	4	7	14	21	28	56	75	84	112	140	168	196	224	252	280	308	336	365
Visit Number	01	02	03	03a	04	05	06	07	08	09	10	11	12	13	14	15	16	17	18	19	20	21
Visit Windows (in days)	N/A	N/A	N/A	N/A	N/A	+/-2	+/-2	+/-2	+/-3	+/-3	+/-5	+/-3	+/-3	+/-3	+/-3	+/-5	+/-5	+/-5	+/-5	+/-5	+/-5	+/-5
Equivalent Week	N/A	N/A	N/A	N/A	N/A	W1	W2	W3	W4	W8	N/A	W12	W16	W20	W24	W28	W32	W36	W40	W44	W48	W52
LOCAL LABORATORY ASSESSMENTS (Con't)																						
EBV IgG	X																					
CMV IgG, CMV IgM		X-yrly 																				X 
Coagulation (PT, PTT, INR)	X	X-yrly	X																			
Blood Type		X 																				
HLA		X																				
Crossmatch		X 																				
Fasting & post-prandial c-pep 				X		X																
Glucose (immediately post-tx)			X 																			
PRA by flow cytometry		X 																				
CMV by PCR		X									X				X							
EBV by PCR 		X																				
CENTRAL LABORATORY ASSESSMENTS																						
First morning spot urine 	X	X							X		X											X
GFR	X	X-yrly							X		X											X
HbA1c	X	X-q3mo									X					X			X			X
Fasting serum gluc/c-pep & creat 	X	X							X	X	X		X	X	X	X	X	X	X	X	X	X
Insulin modified FSIGT 		X-yrly 									X											X
90 min  c-pep/gluc (MMIT) 	X										X					X			X			X
Atherogenic Profile 		X																				X
LOCAL METABOLIC ASSESSMENTS																						
Glycemic Stability (CGMS) 		X 									X											X
BSR eCRFs 	X	X-q6mo									X					X			X			X

Time points (in days relative to transplant)	SCR	WL / BL 	0 	3	4	7	14	21	28	56	75	84	112	140	168	196	224	252	280	308	336	365	
Visit Number	01	02	03	03a	04	05	06	07	08	09	10	11	12	13	14	15	16	17	18	19	20	21	
Visit Windows (in days)	N/A	N/A	N/A	N/A	N/A	+/-2	+/-2	+/-2	+/-3	+/-3	+/-5	+/-3	+/-3	+/-3	+/-3	+/-5	+/-5	+/-5	+/-5	+/-5	+/-5	+/-5	
Equivalent Week	N/A	N/A	N/A	N/A	N/A	W1	W2	W3	W4	W8	N/A	W12	W16	W20	W24	W28	W32	W36	W40	W44	W48	W52	
CALCULATED METABOLIC ASSESSMENTS																							
MAGE		X-q6mo									X					X			X			X	
LI	X	X-q6mo									X					X			X			X	
Clarke Score	X	X-q6mo														X						X	
HYPO	X	X-q6mo									X					X			X			X	
Beta Score		X									X					X			X			X	
C-peptide (gluc X creat) ratio	X	X							X	X	X		X	X	X	X	X	X	X	X	X	X	
IMMUNOSUPPRESSION LEVELS																							
Belatacept trough levels 					X	X	X	X	X	X	X	X	X	X	X	X	X	X	X	X	X	X	X
MECHANISTIC ASSAYS																							
Alloantibody	X	X-q6mo 									X					X			X			X	
Autoantibody 		X									X					X			X			X	
Immunogenicity samples 			X 												X							X	
ARCHIVED SAMPLES																							
Serum		X									X					X			X			X	
Plasma		X									X					X			X			X	

 WL = Waiting List. BL = Baseline. Repeat assessments as indicated (i.e. yrly, q3mo), while subject is on the waiting list. All one-time WL/BL assessments should be completed on Day -2 whenever possible, but always prior to start of immunosuppression. For WL/BL repeat assessments, record results from test done closest to the start of immunosuppression will be used as the baseline value.

 Day 0 = the day of transplant.

 *Informed consent #1* includes information on CIT04 and the multi-center Phase 3 protocol (CIT07)

 *Informed Consent #2* includes information specific to CIT04. IC # 2 must be signed immediately after randomization.

 Retinopathy eval includes fundoscopic pictures for WL/BL assessments and Y1. Screening retinopathy evaluation should be done per site-specific standards. If pupils cannot be dilated, then a manual ophthalmologic evaluation can be substituted.

 These can be collected after subject is considered protocol eligible and has been moved to the transplant wait list, as time allows.

 Chemistry includes: Sodium, albumin, magnesium, chloride, potassium, alk phosphatase, total bilirubin, CO2, creatinine, ALT (SGPT), BUN, gamma GT, glucose, AST (SGOT), calcium, phosphorus

- 
-  Complete serum pregnancy tests within 72 hours prior to initiation of study medication.
-  Complete test prior to Belatacept infusion. Confirm negative result prior to administering Belatacept
-  Serology includes: HBc Ab, HBs Ab, HBs Ag, HCV Ab, and HIV. Do not repeat Hepatitis B tests if HBs Ab was previously positive.
-  Repeat only if previous test was negative.
-  Repeat for subsequent transplant(s)
-  Sample used for crossmatch may be obtained up to 60 days prior to the start of immunosuppression, as long as there is no evidence of infections or transfusions since the time the sample was drawn. Repeat crossmatch for subsequent transplants.
-  C-peptide should be done locally and drawn fasting, and twice between 1-3 hrs post-prandial on Day 3 and Day 7 post-transplant.
-  Finger stick glucose should be done locally and drawn every hour for the first 6 hours immediately post-transplant.
-  Subsequent transplants only. Local result used to determine eligibility for subsequent transplants only.
-  EBV by PCR should only be done post-randomization if reactivation is suspected.
-  First morning spot urine includes: albumin, protein, and creatinine
-  Do not collect for participants with graft failure. Results of tests performed at the time of graft failure will be used for day 75 endpoint calculations.
-  MMTT should include 60 and 90 minute c-peptide and glucose measurements for the screening visit and as necessary when determining graft failure.
-  Atherogenic profile consisting of fasting lipid panel (TG, TC, HDL, LDL, non-HDL), C reactive protein, serum amyloid A, apolipoprotein A1 and apolipoprotein B. If blood is drawn locally, sample should be sent from local lab to study site and then shipped to the central laboratory (Univ of Washington).
-  Blood Sugar Record (BSR) eCRF is completed using information gathered from subject diary logs, glucometer download data, and insulin requirements
-  Complete test prior to Belatacept infusion.
-  For each transplant, complete alloantibody assessment every 6 months and again on Day -2, regardless of the most recent draw. Central PRA result, current within 6 months, is used to determine subject eligibility for first transplant
-  Autoantibody testing includes GAD, IA-2, and IAA.
-  Collect immunogenicity samples prior to belatacept infusion. For subjects that discontinue belatacept, collect additional immunogenicity samples at 4 weeks and 8 weeks post last dose.
-  Collect immunogenicity sample prior to dosing with immunosuppression medications.

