## Study Definitions

Full Graft Function	Islet transplant recipients will be considered to have full islet graft function if they are insulin independent.
Graft Failure	Islet allograft failure will be defined as absence of insulin production by transplanted islets, as evidenced by c-peptide < 0.3 ng/mL. This will be determined by (1) c-peptide < 0.3 ng/mL on random testing, followed by (2) c-peptide < 0.3 ng/mL at baseline, and at 60 and 90 minutes after MMTT. C-peptide levels obtained in the course of the MMTT will be run at the core lab in Seattle, WA; allow 72 hours for results. Participants with graft failure do not need to complete the day 75 metabolic assessments.
Insulin Independent	
Subjects will be considered insulin independent if they are able to titrate off insulin therapy for at least 1 week and all of the following criteria are met:
 

• One HbA1c level, one fasting serum glucose level, and a Mixed Meal Tolerance Test are documented within the visit window (e.g. 70-80 days at Day 75) and 7 consecutive days of blood sugar and insulin readings are documented within +/- 7 days of the visit window (e.g. 63 - 87 days at Day 75);

• HbA1c < 7.0% or ≥ 2.5% decrease from baseline;

• Fasting capillary glucose level should not exceed 140 mg/dL (7.8 mmol/L) more than three times in 7 consecutive days (fasting is defined as 1st blood sugar reading of the day not noted as post-prandial or bedtime);

• Post-prandial serum glucose ≤ 180 mg/dL (10.0 mmol/L) at 90 minutes during the MMTT;

• Fasting serum glucose level ≤ 126 mg/dL (7.0 mmol/L); if the fasting serum glucose level is > 126 mg/dL (7.0 mmol/L), it must be confirmed in an additional one out of two measurements;

• At least one MMTT fasting or stimulated c-peptide ≥ 0.5 ng/mL.

Insulin Dependent	Islet transplant recipients who do not meet the criteria for insulin independence will be considered insulin dependent.
Intensive Diabetes Management	Self monitoring of glucose values no less than a mean of three times each day averaged over each week and by the administration of three or more insulin injections each day or insulin pump therapy.
Partial Graft Function	Islet transplant recipients who do not meet criteria for insulin independence, but have either a basal or stimulated c-peptide level ≥ 0.3 ng/mL (0.1 nmol/L).

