#### 9.1.2.6 B-SCORE: A COMPOSITE INDEX OF POST-TRANSPLANT GRAFT FUNCTION

The  $\beta$ -score will be determined from the HbA1c, insulin requirements, fasting (basal) glucose, and stimulated c-peptide as developed by Ryan et al. The score may range from 0 (no graft function) to 8, with all subjects reported with a score of 8 also having 90-minute glucose levels during a MMTT that are  $\leq 10.0$  mmol/L (180 mg/dL), indicative of excellent graft function.

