#### **10.2.2 Secondary Endpoints**

Secondary endpoints are defined in section 4.1.2. There are a very large number of secondary endpoints so there will be no adjustment for multiplicity. We will not impute values for secondary endpoints but will conduct a sensitivity analysis to determine the potential magnitude of the contributions of the missing values. Details of the sensitivity analysis will be included in the SAP.

Analysis of secondary endpoints will use methods similar to those defined for the primary outcome. When the endpoint is a proportion such as patients achieving insulin independence at one year after completing their first islet transplant then the observed rate will be used as the point estimate and an exact 95% binomial confidence interval will be reported. Continuous variables will be treated in a similar fashion. If the necessary normality assumption is valid then the sample mean will be used as the point estimate and the usual 95% normal confidence intervals will be computed. Where the normality assumptions are not valid and an appropriate transform will achieve normality then the inverse of the mean of the transformed data will be used as the point estimate and the inverse of the endpoints for a standard 95% confidence interval for the transformed mean will be reported for the confidence interval. If no valid

transformation can be found then we will use the bootstrap method to construct a point estimate and a 95% confidence interval.

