## 10.4 Sample Size and Power Calculations

The purpose of this pilot study is to estimate the true rate of insulin independence at 75 days. The selected sample size is 10 subjects. The point estimate of the true insulin independence rate will be the proportion of the 10 patients that achieve insulin independence. The precision of the estimate depends on the observed number of subjects achieving insulin independence. The following table displays the confidence intervals that would be computed for each possible outcome. If 5 of the 10 subjects achieve insulin independence then the estimated rate will be 50% and a 95% confidence interval will be 0.1871 to 0.8129. That is, we are 95% confident that the true rate is at least 18.71% and no more than 81.29%. The confidence interval rules out any rate less than 18.71% or greater than 81.29%. If 3 patients (30%) achieve insulin independence, then the confidence interval will rule out any rate less than 6.67% or greater than 65.25%.

*Table 5: Confidence Intervals for each possible outcomes*

Number of Subjects insulin Independent at 75 Days	Estimated Rate	Exact 95% Confidence Interval	
		Lower Bound	Upper Bound
0	0	0	0.3085
1	0.1	0.0025	0.445
2	0.2	0.0252	0.5561
3	0.3	0.0667	0.6525
4	0.4	0.1216	0.7376
5	0.5	0.1871	0.8129
6	0.6	0.2624	0.8784
7	0.7	0.3475	0.9333
8	0.8	0.4439	0.9748
9	0.9	0.555	0.9975
10	1	0.6915	1

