 Chemistry includes: Sodium, albumin, magnesium, chloride, potassium, alk phosphatase, total bilirubin, CO2, creatinine, ALT (SGPT), BUN, gamma GT, glucose, AST (SGOT), calcium, phosphorus

 Confirm negative result prior to administering Belatacept.

 Also collect as necessary to perform graft failure. Do not collect after graft failure has been confirmed.

 MMTT should include 90 minute c-peptide and glucose measurements, add 60 minute as necessary when determining graft failure.

 Atherogenic profile consisting of fasting lipid panel (TG, TC, HDL, LDL, non-HDL), C reactive protein, serum amyloid A, apolipoprotein A1 and apolipoprotein B. If blood is drawn locally, sample should be sent from local lab to study site and then shipped to the central laboratory (Univ of Washington).

 Blood sugar Record (BSR) eCRF is completed using information gathered from subject diary logs, glucometer download data, and insulin requirements.

 Complete test prior to Belatacept infusion. For pregnancy test, confirm negative result prior to administering Belatacept.

 For each transplant, complete alloantibody assessment every 6 months and again on Day -2, regardless of the most recent draw.

 Autoantibody testing includes GAD, IA-2, and IAA.

 Collect immunogenicity samples prior to belatacept infusion. For subjects that discontinue belatacept, collect additional immunogenicity samples at 4 weeks and 8 weeks post last dose.

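### After graft failure most graft-function tests stop and no value is assigned beyond Day 75, so several Day 365 means rest on functioning grafts only

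*Protocol*

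**What the plan says.** Graft failure is defined by loss of insulin production, "as evidenced by c-peptide < 0.3 ng/mL", and is confirmed by an MMTT sampled at baseline, 60 and 90 minutes. The same definition adds: "Participants with graft failure do not need to complete the day 75 metabolic assessments".

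Appendix 1, footnote 19, is attached to the fasting glucose/C-peptide/creatinine, FSIGT, MMTT, CGMS and blood sugar record rows, and so covers their Day 365 column as well as Day 75. It is not attached to HbA1c. Its second sentence reads: "Results of tests performed at the time of graft failure will be used for day 75 endpoint calculations".

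For subjects with later transplants, Appendix 2, footnote 4, says: "Do not collect after graft failure has been confirmed". Appendix 3, footnote 11, gives the same instruction for Days 75 and 365 after a subsequent transplant. Appendix 4 does so for MMTT and CGMS in the second year. None of the three has a carry rule.

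Section 10.2.2 says: "We will not impute values for secondary endpoints but will conduct a sensitivity analysis". It takes the sample mean as the point estimate for continuous endpoints when normality holds. Section 10.1 applies intention to treat to all primary and secondary analyses, and section 5.7.2 says data from subjects who discontinue, including for graft failure, enter that analysis.

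Appendix 5, the reduced follow-up schedule, lists HbA1c, 90-minute MMTT C-peptide and creatinine at 1 and 2 years after the initial transplant. At 1 and 2 years after the last transplant it lists only SAEs/hypoglycemic events and quality of life.

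**The concern.** The values are missing because the graft failed, which is the outcome these endpoints are meant to describe. If failed grafts have no value and none is assigned, the mean describes graft function among working grafts while being presented as the result for everyone transplanted. The error is in the favourable direction. The planned change from Day 75 to Day 365 after the final transplant also loses every graft that failed in between, which are the largest declines.

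There is a second problem of consistency. A graft that fails before Day 75 after the first transplant has its failure-time results used. One that fails before Day 75 after a second or third transplant does not.

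**Working it through.** **Inputs.** Section 10.4: "The selected sample size is 10 subjects". Graft failure is C-peptide below 0.3 ng/mL (Study Definitions). A beta-score of 0 means no graft function (section 9.1.2.6: "The score may range from 0 (no graft function) to 8"). The number of failures k, and the mean m in functioning grafts, are assumptions, because the protocol gives neither.

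**The plan's own figure.** The protocol states no figure for these means. Its one worked calculation, the exact binomial interval, reproduces: for 5 of 10, "95% confidence interval will be 0.1871 to 0.8129". All eleven rows of Table 5 match to four decimals. They concern the primary endpoint and are not in question.

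**Which endpoints lose failed grafts at Day 365**

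- AIRglu and disposition index: need the FSIGT, which is barred and not in Appendix 5.
- C-peptide ratio: needs fasting glucose and C-peptide (section 9.1.2.7), which are barred. Appendix 5 supplies only creatinine.
- Beta-score: needs insulin requirement and fasting glucose as well as HbA1c and stimulated C-peptide (section 9.1.2.6). The first two are barred.
- 90-minute C-peptide: listed in Appendix 5 at 1 year after the initial transplant, but not at 1 year after a later final transplant.
- Insulin requirement, MAGE, LI, HYPO, insulin sensitivity and CGMS: barred, with no obvious no-function value.

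**Size.** Let f be the value in a failed graft. The functioning-graft mean is m and the all-subject mean is [(10-k)m + kf]/10. With f = 0 the ratio of the two is 10/(10-k):

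- k = 1: 10/9 = 1.11
- k = 2: 10/8 = 1.25
- k = 3: 10/7 = 1.43
- k = 5: 10/5 = 2.00

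Example: a beta-score averaging 6.0 in 7 functioning grafts, with 3 failures at 0, is 7 × 6.0/10 = 4.2 over all 10.

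For 90-minute C-peptide, put failures just under the threshold (f = 0.299 ng/mL) and assume m between 1.5 and 4.0 ng/mL. At k = 2 the all-subject mean is (8 × 1.5 + 2 × 0.299)/10 = 1.26, a ratio of 1.19, or (8 × 4.0 + 2 × 0.299)/10 = 3.26, a ratio of 1.23. At k = 3 the ratios are 1.5/1.14 = 1.32 and 4.0/2.89 = 1.38. So 10/(10-k) is an upper bound, and C-peptide comes in somewhat below it.

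Values of k of 2 or 3 need not trip the numerical study-wide triggers in section 6.2.1 (primary non-function in 3 or more subjects, or 6 consecutive subjects below 0.3 ng/mL at Day 75).

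**The case against.** The strongest reply is that failed grafts are not lost. By Day 365 no further CIT04 transplant is allowed (section 7.5), so a subject with a failed graft should be on Appendix 5. That schedule measures HbA1c, creatinine and 90-minute C-peptide at 1 and 2 years after the initial transplant. This stands: a reader might infer that these subjects go untested at Day 365, and that is wrong for those three measures. But Appendix 5 then contradicts footnote 19, which bars the Day 365 MMTT in the same subjects. It also offers nothing for the FSIGT, fasting or diary measures.

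Second, footnote 19 can be read as a timing rule for observed data, compatible with not imputing. For C-peptide that is fair, since failure is established by an MMTT. If the footnote is followed, the first-transplant Day 75 C-peptide mean includes failed grafts. It does not help FSIGT or CGMS, which are not part of the failure work-up and may leave nothing to carry.

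Third, section 10.2.2 promises a sensitivity analysis, detailed in a SAP not shown here. That would reveal the bias but would leave the headline mean unchanged. The bar on imputation, the carry rule and the collection limits are all fixed in the protocol itself.

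Fourth, the failed-graft value is only partly known. C-peptide is below 0.3, not necessarily 0, and insulin need after failure could exceed baseline. This stands and limits the remedy.

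**Conclusion.** The point holds for the Day 365 means of AIRglu, disposition index, beta-score and C-peptide ratio, for 90-minute C-peptide after a later final transplant, and for the Day 75 to Day 365 change. As written, these rest on functioning grafts only, contrary to section 10.1. The means are overstated by up to 10/(10-k): 1.25-fold at k = 2 and 1.43-fold at k = 3. This assumes k and a no-function value of zero. The ratio does not apply to the change score, for which only the direction is clear.

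Three wider readings are not supported:

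- The primary endpoint is not biased. Section 10.2.1 counts an unevaluated subject as a failure unless a later evaluation exists, and a failed graft cannot meet the 0.5 ng/mL C-peptide criterion for insulin independence.
- The key secondary endpoint is largely protected, because HbA1c carries no footnote 19 and both HbA1c and hypoglycemic events remain in Appendix 5.
- AIRglu and disposition index are not distorted at two years, because section 4.1.2.1 does not list them there. The second-year limits concern MMTT and CGMS.

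**What to change.** Reconcile section 10.2.2, footnote 19 and Appendices 3 to 5 under one analysis rule, applied at each time point where the endpoint exists:

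- Use measured values where available: the failure-time MMTT and the Appendix 5 C-peptide. Do not overwrite them with zero. State whether the MMTT after graft failure follows footnote 19 or Appendix 5, since the two disagree.
- Otherwise enter the no-function value for C-peptide, C-peptide ratio and beta-score, and for AIRglu and disposition index at Days 75 and 365 only.
- Keep failures in the denominator, print their number beside each mean, and give the observed-only mean as a sensitivity analysis.
- For insulin requirement, insulin sensitivity, CGMS, MAGE, LI and HYPO, report the observed mean labelled as functioning grafts only, with the number of failures beside it. Do not assume a 0% insulin reduction.

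The cost is wording in the protocol and SAP, with no new data. Section 10.5 requires an amendment if these count as principal features. Zeros may break normality and rule out a log transform, but section 10.2.2 already provides the bootstrap for that case. The reported means will be less favourable.
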